#### SDOH Supplement:

We anticipate generating descriptive data characterizing the outer contextual environment of the ISC3 network across the seven identified domains. Our overall analytic approach for this will consist of summarizing SDOH measures using descriptive statistics and data visualization methods to characterize the outer context across CHCs in our laboratories. We will examine the relationship between outer context and cancer prevalence, cancer-related behaviors, and policies across the ISC3 network, likely at the zip code and state level, since this would reflect the local and state-level policy context. We will examine the relationship between the seven contextual domains and cancer prevention behaviors (e.g. are cancer preventive behaviors better in jurisdictions that have lower levels of food and housing insecurity and other social needs?), and cancer-relevant policies (e.g. are cancer-relevant policies more prevalent in jurisdictions with more or fewer social needs?). We also anticipate comparing SDOH and health outcomes across several Centers at the relationship between outer context and cancer prevention outcomes, with analyses conducted at the practice-level. For example, we will assess the association between outer context measures and practice variation in rates of cervical and colorectal cancer screenings and smoking cessation intervention in practices located in specific states, including within and across state variation using multi-level modeling.

We will also collect survey responses from clinicians and patients to investigate the relationships between cancer screening tests and being referred for, accepting or declining these tests.

## 9.2 SAMPLE SIZE DETERMINATION

Using the approach described by Hussey, et. al, we find that our proposed sample size (n=108) will provide >80% power to detect a .91 effect size difference between controls and intervention patients on continuous outcomes. While this study is not powered to detect smaller differences, it will be useful to obtain estimates of means, variability, and intraclass correlation for key outcomes to aid in planning the future study.

We have since added calculation for the Phase 2 trial and our proposed sample size of 216 participants will provide >80% power to detect a .58 effect size. Being a pilot, this feasibility data will be sufficient to lead to a larger trial aimed to produce a greater effect.

## 9.3 POPULATION FOR ANALYSES

1. Patients: Age 50 - 80; English or Spanish speaking, asymptomatic; tobacco smoking history of 20+ pack-years; current smoker or quit within last 15 years.
2. Clinicians: Age 18-100; English or Spanish speaking; Physicians and advanced practice providers
3. Staff: Age 18-100; English or Spanish speaking; Nurses, administrators, medical assistants, social workers, and other clinic personnel.
4. Leaders of rural clinics, hospitals, and radiology sites serving patients from the rural clinics; Age 18-100; English or Spanish speaking.

ADRD Supplement:

1. Patients: Age 55+; English or Spanish speaking, Diagnosis of dementia in the medical record [e.g., Alzheimer's disease, vascular dementia, dementia associated with Parkinson disease, dementia NOS (not otherwise specified), etc.].
2. Care Partners: Age 45+; English or Spanish speaking, care partner of a person with ADRD defined as family member, non-paid companion, or a designated health care proxy

SDOH Supplement:

As above with slight modifications:

1. Patients: Age 45+; Seen in one of the clinic practices in the supplemental funding period.
2. Clinicians: Physicians and advanced practice providers

## 9.4 STATISTICAL ANALYSES

### 9.4.1 GENERAL APPROACH

Analysis of qualitative data will be a continuous process beginning with initial interviews and continuing throughout and beyond the data generation period.

### 9.4.2 ANALYSIS OF THE PRIMARY EFFICACY ENDPOINT(S)

A multidisciplinary team led by Drs. [name] and [name], and guided by [name] will begin the analysis process with repeated readings of the transcripts to achieve immersion. The team will then develop and apply a list of codes using an emergent rather than a priori approach, to emphasize interviewee perspectives and de-emphasize team member speculations. All coded data will be entered into ATLAS.ti v 8.0 (GmbH, Berlin) for data management. Coded transcripts will be analyzed by the qualitative analyst within and across sites and settings to develop the major themes or concepts reported. The trustworthiness of study results will be enhanced through triangulation of the data and an “audit trail” throughout the data collection and analysis process. Analysis results will inform both the design of the implementation for the second study phase, and the initial methods projects.

RedCap or similar software will be used to conduct surveys and store survey data. The same team (above) with the addition of [name] will lead the quantitative analysis. Multiple outcomes from each individual on the five RE-AIM outcomes will produce repeated measures as we wish to compare ratings across outcomes; general linear mixed models can accommodate both levels of clustering. Since primary effects of interest are between individuals within clinics (or within individuals), the intraclass correlation coefficient will have less impact than in the case of between-clinic comparisons and is not considered here. Adjusted for multiple comparisons (providers vs. staff vs. patients), a sample size of 6 to 10 individuals per clinic (2 - 3 providers, 2 - 3 staff, 2 - 3 patients) from 80 clinics (160 to 240 per stakeholder type, 480 to 720 total) will provide a power of >80% to detect an effect size of 0.3 SD to .37 SD. For differences across respondent types on a single RE-AIM dimension. For the RE-AIM dimensions within individuals, adjusted for multiple comparisons, this sample size will provide .80 power to detect a .24 to .30 effect size difference between any two RE-AIM outcome dimensions.

In Phase 2, no less than 9 patients per clinic per step and 2-3 practice staff from up to 6 clinics will provide a power of >80% to detect a effect size of 0.58. SD will vary depending on final number of clinics enrolled. Being a small feasibility trial, we will enroll clinics up to 6, to achieve our goal of understanding feasibility of the use of our PtDA in a larger, national trial.

SDOH Supplement:

We will conduct separate models for different cancer preventive care outcomes as the outer context may have differential impact. We will consider random effects for state to account for clustering, and will utilize several statistical criteria to determine relative contributions of multi-level factors, including but not limited to: interpretations of measures of relative risk (e.g., odds ratios, rate ratios) and effect sizes, statistical significance, explained variation for GLMMs, and model diagnostics. Paired survey data will be analyzed primarily using descriptive statistics.

---

#### **9.4.3 ANALYSIS OF THE SECONDARY ENDPOINT(S)**

N/A

---

#### **9.4.4 SAFETY ANALYSES**

N/A

---

#### **9.4.5 BASELINE DESCRIPTIVE STATISTICS**

N/A

---

#### **9.4.6 PLANNED INTERIM ANALYSES**

N/A

---

#### **9.4.7 SUB-GROUP ANALYSES**

N/A

---

#### **9.4.8 TABULATION OF INDIVIDUAL PARTICIPANT DATA**

N/A

---

#### **9.4.9 EXPLORATORY ANALYSES**

N/A

---

### **9.5 ENROLLMENT/RANDOMIZATION/MASKING PROCEDURES**

Project #1 - Shared Decision Making in Lung Cancer Screening and Smoking Cessation Intervention: We considered three potential designs for this trial. A classic patient-level randomization is not ideal since practices (rather than patients) are the primary targets. A traditional cluster randomized trial would be disadvantaged by the small number of sites. Therefore, we propose a multicenter trial with a pre-post design where all the groups will receive the intervention. This design has been effectively used with rural Colorado PBRN practices. We propose a pilot study using a pre-post design with two time blocks of approximately 3 months each (Table 2) and will enroll approximately 36-48 patients per practice over a 12-month period for a total of 144-192 patients across all four practices. We will not exceed 6 practices and 216 patients.

SDOH Supplement: No randomization planned.

## 10 SUPPORTING DOCUMENTATION AND OPERATIONAL CONSIDERATIONS

### 10.1 REGULATORY, ETHICAL, AND STUDY OVERSIGHT CONSIDERATIONS

#### 10.1.1 INFORMED CONSENT PROCESS

Participants will be consented using an IRB approved post card consent form with verbal consent before enrolling.

##### 10.1.1.1 CONSENT/ASSENT AND OTHER INFORMATIONAL DOCUMENTS PROVIDED TO PARTICIPANTS

###### **REQUIRED TEXT:**

Consent forms describing in detail the study procedures, and risks will be offered to the participant and written documentation of informed consent is required prior to starting intervention/administering study.

##### 10.1.1.2 CONSENT PROCEDURES AND DOCUMENTATION

###### **REQUIRED TEXT:**

Informed consent process will be initiated prior to the individual's agreeing to participate in the study and continues throughout the individual's study participation. Extensive discussion of risks, though minimal and possible benefits of participation will be provided to the participants and their families.

Consent forms will be IRB-approved and the study team will read and review the document with the participant. The investigator will explain the research study to the participant and answer any questions that may arise. All participants will receive a verbal explanation in terms suited to their comprehension of the purposes, procedures, and potential risks of the study and of their rights as research participants. Participants will have the opportunity to carefully review the consent form and ask questions prior to consenting. The participants will have the opportunity to discuss the study with their surrogates or think about it prior to agreeing to participate. The participant will sign the informed consent document or give verbal consent via audio recording prior to any procedures being done specifically for the study.

**ADRD Supplement:**

For individuals with diagnosis of ADRD, the informed consent process will use a functional demonstration of decision making capacity through a teach-back method. The “teach-back” method maximizes the ability of older adults with early dementia to participate and protects those individuals who cannot “teach-back” consent information in their own words.

The participants may withdraw consent at any time throughout the course of the trial. A copy of the informed consent document will be offered to the participants for their records. The rights and welfare of the participants will be protected by emphasizing to them that the quality of their medical care will not be adversely affected if they decline to participate in this study.

The study allows the inclusion of Spanish speaking and non-reading participants. Witnesses to these consent processes will be individuals not associated with the trial and will not have a conflict of interest.

SDOH Supplement: Same as center above.

---

**10.1.2 STUDY DISCONTINUATION AND CLOSURE**

We do not anticipate discontinuation of these pilots.

---

**10.1.3 CONFIDENTIALITY AND PRIVACY**

**REQUIRED TEXT:**

Participant confidentiality is strictly held in trust by the participating investigators, their staff, and the sponsor-investigator(s) and their agents. Therefore, the study protocol, documentation, data, and all other information generated will be held in strict confidence. No information concerning the study or the data will be released to any unauthorized third party without prior written approval of the sponsor.

The study monitor, other authorized representatives of the sponsor-investigator, or representatives of the IRB may inspect all documents and records required to be maintained by the investigator, including but not limited to, medical records (office, clinic, or hospital) for the participants in this study. The clinical study site will permit access to such records.

The study participant's contact information will be securely stored at each clinical site for internal use during the study. At the end of the study, all records will continue to be kept in a secure location for as long a period as dictated by local IRB and Institutional regulations.

Study participant research data, which is for purposes of statistical analysis and scientific reporting, will be transmitted to and stored on the secured server at the University of Colorado's Adult and Child Consortium for Health Outcomes Research and Delivery Science. This will not include the participant's contact or identifying information. Rather, individual participants and their research data will be identified by a unique study identification number. At the end of the study, all study databases will be de-identified and archived at the University of Colorado Cancer Center.

---

#### **10.1.4 FUTURE USE OF STORED SPECIMENS OR DATA**

##### **REQUIRED TEXT :**

Data collected for this study will be analyzed and stored on the secured server at ACCORDS, under the supervision of the Program Manager, for use by other researchers including those outside of the study. Some data may be shared or collaborated upon using the University's Egnyte server, a HIPAA compliant, cloud based server service provided by the university.

---

#### **10.1.5 KEY ROLES AND GOVERNANCE**

Data collected for this study will be analyzed and stored on the secured server at ACCORDS, under the supervision of the Program Manager, for use by other researchers including those outside of the study. Some data may be shared or collaborated upon using the University's Egnyte server, a HIPAA compliant, cloud based server service provided by the university. Egnyte automatically compiles a log of changes to data detailing who made changes and when they were made.

If preferred, practices can fax their patient lists versus sharing via Egnyte. Faxes can be sent to the Department of Family Medicine (DFM) fax line. In accordance with HIPAA regulations, practices will use a cover sheet. The fax will be addressed to a member of the study team that is part of the High Plains Research Network (HPRN), which is housed in DFM. The HPRN study team will coordinate with practices choosing to fax information to ensure a member of the team is present to receive the fax and to confirm receipt. The fax will be scanned, and the electronic version will be saved on Egnyte. Hard copies will be locked in a cabinet in the study team member's office, which is also locked. Hard copies will be shredded upon completion of recruitment.

---

#### **10.1.6 SAFETY OVERSIGHT**

## REQUIRED TEXT FOR SINGLE-SITE STUDIES:

### **Non-Interventional IIT (No Additional Risk)**

The principal investigator will be responsible for the conduct of this study, overseeing participant safety, executing the data and safety monitoring (DSM) plan, and complying with all reporting requirements to local and federal authorities. This oversight will be accomplished through additional oversight from the Data and Safety Monitoring Committee (DSMC) at the University of Colorado Cancer Center (CU Cancer Center). The DSMC is responsible for ensuring data quality and study participant safety for all trials at the CU Cancer Center. A summary of the DSMC's relevant activities is as follows:

- Conduct of internal audits
- May submit recommendations for corrective actions to the CU Cancer Center's Executive Committee

Study audits conducted by the DSMC will consist of a review of the regulatory documents, consent forms, and source data verification. Documentation of the audit conducted by the DSMC will then need to be submitted to the IRB of record at the time of the IRB's continuing review of this trial (if applicable).

---

### **10.1.7 CLINICAL MONITORING**

#### **REQUIRED TEXT:**

Clinical site monitoring will be conducted to ensure that the rights and well-being of human participants are protected, that the reported trial data are accurate, complete, and verifiable, and that the conduct of the trial is in compliance with the currently approved protocol/ amendment(s), with GCP, and with applicable regulatory requirement(s). Monitoring for this study will be performed by ACCORDS staff in accordance with the clinical monitoring plan (CMP).

---

### **10.1.8 QUALITY ASSURANCE AND QUALITY CONTROL**

#### **REQUIRED TEXT:**

Quality Control (QC) procedures will be implemented beginning with the data entry system and data QC checks that will be run on the database will be generated. Any missing data or data anomalies will be communicated to the site(s) for clarification/ resolution.

Following written SOPs, the study monitor will verify that the clinical trial is conducted and data are generated, documented (recorded), and reported in compliance with the protocol, GCP, and the applicable regulatory requirements.

The investigational site will provide direct access to all trial-related sites, source data/ documents, and reports for the purpose of monitoring and auditing by the DSMC audit team, and inspection by local and regulatory authorities.

---

### 10.1.9 DATA HANDLING AND RECORD KEEPING

Data handling and record keeping will be done within a secured Egnyte file-sharing platform. This storage is IRB/HIPAA compliant and encrypted.

Any faxed data will be locked in a secure location within Academic Office 1 and will be shredded upon the culmination of the pilot work.

---

#### 10.1.9.1 DATA COLLECTION AND MANAGEMENT RESPONSIBILITIES

##### **REQUIRED TEXT:**

Data collection is the responsibility of the clinical trial staff at the site under the supervision of the site PI. The PI is responsible for ensuring the accuracy, completeness, legibility, and timeliness of the data reported.

---

#### 10.1.9.2 STUDY RECORDS RETENTION

##### **REQUIRED TEXT:**

Study documents will be retained for a minimum of 7 years per HIPAA regulations. These documents will be retained for a longer period, however, if required by local regulations or institutional policies. No records will be destroyed without the written consent of the sponsor-investigator.

---

#### 10.1.10 PROTOCOL DEVIATIONS

##### **REQUIRED TEXT:**

A protocol deviation is any noncompliance with the clinical trial protocol, GCP, or SOP requirements. The noncompliance may be either on the part of the participant, the investigator, or the study site staff. As a result of deviations, corrective actions are to be developed by the site and implemented promptly. These practices are consistent with ICH E6, sections:

- 4.5 Compliance with Protocol, sections 4.5.1, 4.5.2, and 4.5.3.
- 5.1 Quality Assurance and Quality Control, section 5.1.1.

- 5.20 Noncompliance, sections 5.20.1 and 5.20.2.

It is the responsibility of the study team to use continuous vigilance to identify and report deviations within 7 working days of identification of the protocol deviation, or within 30 working days of the scheduled protocol-required activity. All deviations must be addressed in study source documents, reported to the DSMC and COMIRB. Protocol deviations must be sent to the local IRB per their guidelines. The site PI/ study staff is responsible for knowing and adhering to their IRB requirements. Further details about the handling of protocol deviations will be included in the -SOP and/or study procedures manual.

---

#### 10.1.11 PUBLICATION AND DATA SHARING POLICY

**REQUIRED TEXT:**

This study will ensure that the public has access to the published results of this research, and also meet obligations of the NCI funder.

---

#### 10.1.12 CONFLICT OF INTEREST POLICY

**REQUIRED TEXT:**

Independence of this study from any actual or perceived influence, such as by the pharmaceutical industry, is critical. Any actual conflict of interest of persons who have a role in the design, conduct, analysis, publication, or any aspect of this trial will be disclosed and managed by the University of Colorado Denver's (UCD) Office of Regulatory Compliance Conflict of Interest and Commitment Management (COIC) program. Persons with a perceived conflict of interest will have such conflicts managed in a way that is appropriate to their participation in the trial. Conflict of Interest management plans are project-specific and are reviewed at least annually. UCD has integrated the institutional conflict of interest management program with its existing program.

---

#### **Project Plan - Alzheimer's disease supplement**

**Lay Summary:** What are the experiences of persons with mild cognitive impairment/early dementia, family care partners, and primary care team members in rural areas related to:

- a) risks, benefits, burdens of cancer prevention and screening (such as lung cancer screening, colon cancer screening, and smoking cessation) (all stakeholders);
- b) communication and shared decision making, especially in the context of cognitive impairment and involvement of care partners (all);
- c) barriers to screening and dementia care services in rural areas (care partner, primary care perspectives)
- d) if/how primary care processes for colon/lung cancer screening are adapted to meet the needs of patients/ families living with dementia (primary care stakeholder perspectives)?

#### **Settings**

At least four rural primary care clinics that have the capacity to identify patients with Alzheimer's disease and related dementias (ADRD), care partners, and primary care stakeholders. We plan to engage two HPRN clinics that have a high prevalence of older patients (which may have more colon cancer screening experience) and two NRN practices (which have more lung cancer screening experience)

#### **Participants**

- **Patients** with mild cognitive impairment (MCI)/early dementia (3-4 per clinic)
- **Care partners** of those with MCI/early dementia (3-4 per clinic; recruited as dyads; interview sequentially)
- **Care partners** of patients with advanced dementia (2-3 per clinic)
- **Primary care clinicians** (MD, NP, PA) (2-3 per clinic); **primary care team members** (care managers, RN, SW) (2-3 per clinic)

### **Eligibility**

Patients with mild cognitive impairment/early dementia AND decision making capacity, defined as the ability to provide informed consent to study participation (n=12-16 patients in total, or 3-4 per clinic) with the following inclusion criteria:

- Age 55+; English or Spanish speaking,
- Seen in one of the clinic practices in the past year, and
- Diagnosis of dementia in the medical record [e.g., Alzheimer's disease, vascular dementia, dementia associated with Parkinson's disease, dementia NOS (not otherwise specified), etc.].

Care partners, defined as someone the patient agrees to as their study partner, such as a family member, non-paid companion, or a designated health care proxy. (n=20-26 care partners in total)

- Care partner of a patient with early dementia who has the ability to provide informed consent (12-16 care partners, as part of patient-care partner dyads). These care partners will be recruited with the patient.

OR

- Care partner of a person with dementia who lacks decision making capacity to provide informed consent to participate in the study (n=8-10 care partners, or 2-3 per clinic). These care partners will be directly recruited, and then the person with ADRD (if available) can participate by providing assent.

Primary care stakeholders (n=25, or approximately 4-6 clinicians or staff based on clinic size):

- Clinicians (n=8-12): Physicians and advanced practice providers
- Staff (n=8-12): Social workers, case managers, nurses, clinic administrators, or others.

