**Objectives:**

**• Primary Objective:**

1. We will use qualitative and quantitative methods to assess the availability and existing infrastructure related to lung cancer screening (LCS) in rural areas. Using this information, we will develop a patient decision aid (PtDA) for lung cancer screening (LCS) and implement in Colorado rural primary care (State Networks of Ambulatory Practices and Partners, SNOCAP) after rapid-cycle design prototyping. In later years, results will be replicated in a national primary care network, National Research Network.
2. We will refine our published cost capture template to categorize costs associated with the various RE-AIM outcomes and pilot test the revised templates in three local primary care practices varying on size, geographic location, and history of involvement in PBRN research that are delivering LCS and smoking cessation services.
3. A. Through qualitative interviews and surveys, we will strive to understand the perspectives and values rural stakeholders

hold about LCS. We will establish the perceived costs and benefits of using shared decision making in LCS and LCS itself.

3. B. *Develop and pilot a brief survey of preferences related to the relative importance of RE-AIM outcomes (e.g., reach, implementation, maintenance) to assess benefits of various RE-AIM outcomes across stakeholders (patients, providers, and staff). Assess relationships between RE-AIM outcome preferences and selection of different CPC programs. Use rapid human-centered design procedures to develop and pilot a graphical value feedback display*
4. A. Identify experiences related to shared decision making for cancer prevention and control activities in rural primary care settings from the perspective of patients with mild cognitive impairment or early dementia, care partners of persons with dementia, and primary care stakeholders (health care provider or staff member).
4. B. Identify how primary care clinics adapt shared decision making or communication approaches to cancer screening and smoking cessation to meet the specific needs of patients and care partners affected by dementia.
- 5 A. Conduct an environmental scan of SDOH within site-specific geographic areas and supplement the cross-ISC3 standard data extraction.
- 5 B. Survey clinician-patient dyads during wellness-focused visits to evaluate the influence of SDOH on cancer prevention and screening decision processes among primary care clinicians and patients.

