## 5 STUDY POPULATION

### 5.1 INCLUSION CRITERIA

#### REQUIRED TEXT:

In order to be eligible to participate in this study, an individual must meet all of the following criteria 1-4 and at least one of the criteria 5-9:

1. Provision to sign and date the consent form.
2. Stated willingness to comply with all study procedures and be available for the duration of the study.
3. All participants: Be a Male or Female aged 18 – 100 (50-80 for patients)
4. All participants: English or Spanish speaking

5. Patient participants: Asymptomatic; tobacco smoking history of 20+ pack-years; current smoker or quit within last 15 years
6. Clinicians: Physicians or advanced practice providers
7. Staff: Nurses, administrators, medical assistants, social workers, or other clinic personnel.
8. Leaders of rural clinics, hospitals, or radiology sites serving patients from the rural clinics. Care partner participants: patient family member, non-paid companion, or a designated health care proxy

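### The Alzheimer's supplement requires capacity of its patients, then admits people who lack it by assent, and the protocol text asks for no authorised permission

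*Combined protocol and SAP*

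**What the plan says.** The supplement's Eligibility section defines its patient group as "Patients with mild cognitive impairment/early dementia AND decision making capacity, defined as the ability to provide informed consent to study participation", with 12-16 planned. It then describes two kinds of care partner. The second kind is "Care partner of a person with dementia who lacks decision making capacity to provide informed consent to participate in the study", with 8-10 planned. Of this second kind it says: "These care partners will be directly recruited, and then the person with ADRD (if available) can participate by providing assent".

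A care partner is defined there as "someone the patient agrees to as their study partner, such as a family member, non-paid companion, or a designated health care proxy". Proxy status is therefore one possibility among several and not a condition.

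Section 5.1 requires every individual to meet criteria 1 to 4. Criterion 1 reads "Provision to sign and date the consent form". The ADRD paragraph of 5.1 keeps all the general criteria and adds conditions. Its patient line does not mention capacity.

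For people with an ADRD diagnosis, Section 10.1.1.2 and the supplement's informed-consent section use a teach-back check. It "maximizes the ability of older adults with early dementia to participate and protects those individuals who cannot" restate the consent information in their own words.

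**The concern.** The Eligibility section sets capacity as a condition for patients and, a few lines later, opens a route for people who by its own description do not have it. A site that follows the second statement would include someone who cannot consent, and nothing in the protocol text tells the site whose permission it needs.

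The care partner on this route is recruited and consented for his or her own participation. He or she may be a relative or companion with no authority to decide for the other person. Missing permission cannot be put right after the interview has taken place, so the gap needs closing before anyone is approached this way.

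**Working it through.** No statistical figure in the plan bears on this point. The check is a comparison of passages and a head count.

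**1. Inside the supplement plan**

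| Place | People who lack capacity |
|---|---|
| Participants | For advanced dementia, only care partners are listed |
| Eligibility, patient paragraph | Excluded: capacity is required |
| Eligibility, second care-partner bullet | May take part by assent, if available |

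The third row cannot be reconciled with the first two as written.

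**2. Against the core protocol**

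- 5.1, criterion 1: consent is mandatory for every individual. The ADRD paragraph of 5.1 inherits it and gives no exception.
- 10.1.1: postcard form with verbal consent.
- 10.1.1.1: written documentation of consent. The heading mentions assent, but no assent procedure follows.
- 10.1.1.2: signature or audio-recorded verbal consent by the participant.

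These sections disagree on signed versus verbal consent, which is a separate matter. All of them call for the participant's consent, and none accepts assent in its place.

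**3. Who gives permission for the person**

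- 10.1.1.2 mentions surrogates once, as people with whom a participant may discuss the study.
- The ADRD part of 10.1.1.2 provides witnesses for Spanish-speaking and non-reading participants. A witness does not give permission.
- The supplement's informed-consent section says care partners will be consented. It says nothing about consent on another person's behalf.
- Section 2.2 says care partners often act as surrogate decision makers, which implies that some do not.

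The visible text therefore contains no requirement for authorised permission.

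**4. How many people**

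Inputs, all from Eligibility: 12-16 patients with capacity, 12-16 care partners paired with them, and 8-10 care partners of people without capacity.

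- Check on the plan's total: 12 + 8 = 20 and 16 + 10 = 26, which matches the stated 20-26 care partners.
- The per-clinic rate gives a slightly wider range: 2-3 per clinic × 4 clinics = 8-12, against the stated 8-10. The difference does not affect the point.
- Upper bound, one person per care partner, all available and all assenting: 8-10 people.
- Share of all participants with cognitive impairment or dementia at that bound: 8/(8 + 16) = 33% to 10/(10 + 12) = 45%.
- Lower bound: 0, because the plan sets no target for this group.

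**The case against.** The strongest reply is that the gap rests on silence. The consent forms were removed before this review and could carry a representative's signature line. The documents nowhere say that surrogate permission is waived. This stands as a limit on the wording: the supportable claim is that the protocol text does not require authorised permission, not that the study will proceed on assent alone. It does not remove the conflicts within Eligibility, with Participants, or with criterion 1.

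A second reply is that the exposure is small: an optional addition, with no planned number, to a qualitative supplement described as minimal risk. No endpoint, sample size or quantitative analysis depends on it. That is fair on size and is why 8-10 is given only as a ceiling.

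Several stronger readings are tempting, but the documents do not support them:

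- A reader might infer that the assent route flatly contradicts teach-back. The text says teach-back protects people who fail it, not that they are excluded. It could be a way of sorting people between two routes. What is missing is a stated consequence of failing.
- A reader might infer that these interviews serve no objective, since Objective 4A asks for the view "from the perspective of patients with mild cognitive impairment or early dementia, care partners of persons with dementia". But Objective 4B concerns adaptation for patients and care partners affected by dementia without limiting the stage, and Sections 1.3 and 4.2 add the level of dementia as a topic of interest. The interviews could serve those aims.
- A reader might infer that a site using 5.1 alone would enrol such a person, because its ADRD patient line names no capacity requirement. Criterion 1 is inherited there, so 5.1 alone would stop enrolment.
- A reader might infer that the data would have to be discarded. Nothing in the documents says so.
- A reader might make much of "Care partners, defined as someone the patient agrees to as their study partner", since a person without capacity cannot readily agree to a partner. The informed-consent section asks only patients able to consent to name one, and Section 9.3 defines care partners without patient agreement. What remains is a loose definition.

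**Conclusion.** The point holds in this form. The supplement's Eligibility section both excludes and admits people who lack decision-making capacity. The admitting sentence conflicts with the supplement's Participants list and with the inherited consent criterion in 5.1. The protocol text requires no authorised permission for these people, and the accompanying care partner need not hold any authority.

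At most about 8-10 people are affected, or 33% to 45% of participants with cognitive impairment or dementia. Both figures assume that every such person is available and assents; the plan supports anything from zero up to that. The conclusion about permission rests on the protocol text alone, since the consent forms were not seen. The conflicts between sections do not depend on the forms.

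**What to change.** Reconcile Section 5.1 (criterion 1 and the ADRD paragraph), the ADRD part of 10.1.1.2, and the supplement's Participants, Eligibility and informed-consent sections by one of two routes:

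- **(a) Care partner only.** Delete the assent sentence, so that for people who lack capacity only the care partner takes part, as Participants already has it.
- **(b) Assent plus permission.** Keep the sentence, but allow assent only where a designated health care proxy or other legally authorised representative also documents permission for the person. Add the matching exception to criterion 1, extend Participants to include these people, and say how assent and dissent are recorded. "Legally authorised representative" is a term of this proposal; the plan does not use it.

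Under either route, state in the ADRD paragraph of 5.1, in 10.1.1.2 and in the supplement's informed-consent section that a person who does not pass teach-back is not enrolled through the patient-consent route. If the consent forms already provide for a representative's permission, bring that rule into the protocol text.

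The cost is wording in the protocol and consent script. The downside is that some people with advanced dementia would not be interviewed: all of them under (a), and those without an authorised representative's permission under (b). The 8-10 care-partner interviews are unaffected.
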